2.2 ENDPOINTS

2.2.1 Primary Endpoint

- Proportion of participants achieving urate level $\leq 0.30\text{mmol/L}$ at 24 weeks.

2.2.2 Secondary Endpoints (assessed at week 24 and 52, and for extension study also at week 104 and 156)

- Proportion of participants achieving urate level $\leq 0.3\text{mmol/l}$ and $\leq 0.36\text{mmol/l}$
- Prospectively gathered number of days of self-reported gout flare over course of study
- Size in mm of the largest tophus at baseline (index tophus)
- The number of clinically evident tophi
- Prospectively gathered self-reported quality of life during/following gout flare evaluated using the EQ-5D-5L questionnaire over course of study
- Prospectively gathered data on days lost at work due to gout flare over course of study
- Prospectively gathered number of scheduled and unscheduled medical appointments/ hospital admissions due to gout over course of study
- Self report of number of doses of medication omitted in preceding 2 weeks will be collected at all study visits
- Plasma oxypurinol levels will be measured at study visits where possible
- Proportion of patients achieving a dose reduction of urate lowering therapy in the extension phase whilst maintaining target urate levels.
- Proportion of patients achieving sustained dietary modifications with reduction of urate levels, and/or further reduction of urate lowering therapy dose in the extension phase.

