6.1.2 Intervention procedures

Based on the baseline renal function and serum urate levels, and in line with local protocols, an individual treatment plan will be drawn up for all participants in both groups. This includes a management plan for a potential episode of gout-flare and offering of flare prophylaxis. The treatment plan will be sent to the general practitioner and the patient copied in. All participants will be examined at baseline and the number and size of tophi (if present) will be recorded.

All participants will have the GoutSMART application installed on their phones, and be taught how to use the application to allow direct communication between the research staff and the participant. All participants will be given access to online resources providing background information on the causes of gout, the likely progression of symptoms, strategies for dealing with acute attacks of gout and the importance of controlling serum urate levels. All participants will be prompted once per month to enter information about their disease severity including the number of days of flare per month, health related quality of life during and after flares, number of days lost at work and the number of health care appointments attended.

Participants in the intervention group will receive their treatment plan in the same fashion and will be provided with the BeneCheck hand-held device, taught to perform the serum urate finger prick self-test and shown how to enter this information into the application. Participants will be sent automatic reminders two weeks after any increased dose of urate lowering therapy (including that of the plan set during baseline clinic consultation) to test their own urate levels and submit updated readings. If urate levels remain above target, written advice to increase the dose of urate lowering will be sent to the patient and supervising physician advising up-titration of therapy, with this confirmed also by text message. If up-titration is recommended, a reminder to test again will be sent after a further two weeks. Conversely, for participants achieving target levels, acknowledgement will be sent and a request to resubmit readings will be sent on a monthly basis until three consecutive target readings have been obtained. Six months are allowed to ensure that all participants have the opportunity to escalate to maximum therapy and potentially switch to alternative urate lowering therapy if required.

6.1.3 End-of study visit week 24

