6.2.3 App assessments

The smart phone application will collect the following data monthly over the 52 weeks of the study

- Number of days of self-reported gout flare
- Self-reported quality of life during/following gout flare evaluated using the EQ-5D-5L questionnaire
- Number of days lost at work due to gout flare
- Number of scheduled and unscheduled medical appointments/ hospital admissions due to gout

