7 DATA COLLECTION

Data will be collected at baseline, week 24 and 52 visits as well as via the smart phone application on a monthly basis. Data will be collected by the principal investigator and the sub-investigators. We will use the EQ-5D® standardized instruments EQ-5D-5L to evaluate health outcome. To maximise completeness of data collection, every effort will be made to contact participants who have failed to attend scheduled visits, submit requested information via the smart phone application or return questionnaires. Participants will be contacted by telephone on at least two occasions.

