8.2 PROPOSED ANALYSES

The primary outcomes of the study will be the proportion of participants achieving urate level $\leq 0.3\text{mmol/l}$ at 24 weeks in participants receiving supported self-management compared to those receiving usual care. Comparison of proportions will be performed using the Chi-square test of independence, or Fishers Exact test for where expected values in any cell of the contingency table are less than 5, with results displayed as frequency (percentages). The proportion of participants achieving serum urate level $\leq 0.3\text{mmol/l}$ at all subsequent assessments will be analysed in the same fashion. Patients with undetectable levels of oxypurinol will be deemed to be non-compliant and a similar analysis will compare the proportion of participants in each treatment allocation that are non-compliant. For these analyses an intention to treat analysis will be performed with participants that have dropped out of the study being included as failing to reach target, or non-compliant with medication respectively.

Continuous outcome measures include the size in mm of the largest tophus at baseline (index tophus) measured at 52 weeks, and the number of clinically evident tophi evaluated at 52 weeks. Further continuous outcomes include the number of days lost at work due to gout flare, number of scheduled and unscheduled medical appointments/ hospital admissions, self report of number of doses of medication omitted in 2 weeks prior to study visits at week 24 and 52. Two-tailed independent student t-tests will be applied for between group comparisons of normally distributed data. Results will be displayed as mean \pm standard deviation (SD). A Mann Whitney U test (MWU) will be applied when the variables are not normally distributed, with results given as median (interquartile range IQR). Although a nominal value of significance of $p<0.05$ for these exploratory measures will be adopted, given the number of secondary outcomes listed a Bonferroni correction will be applied and reported alongside each result.

Although health reported quality of life data will be gathered this is exploratory data that will not be analysed directly but be used to inform the design of a larger health economic study.

Statistical analysis will be performed using Minitab version 16 (Minitab Inc., Pennsylvania, US) or the Statistical Package for Social Services version 19 (SPSS IBM Corp, NY State, US).

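### Section 8.2 compares work days lost and appointments between arms with no allowance for dropout or missed monthly app entries, and lists no analysis of flare days

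*Combined protocol and SAP*

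**What the plan says.** **Outcomes and tests.** Section 8.2 treats counts as continuous measures: "Further continuous outcomes include the number of days lost at work due to gout flare", followed by "number of scheduled and unscheduled medical appointments/ hospital admissions, self report of number of doses of medication omitted". The tests are "Two-tailed independent student t-tests will be applied for between group comparisons of normally distributed data" and otherwise "A Mann Whitney U test (MWU) will be applied when the variables are not normally distributed". Neither has a term for time observed.

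**How the data arise.** Section 6.2.3: "The smart phone application will collect the following data monthly over the 52 weeks of the study". Work days lost and appointments or admissions are on that list, and 2.2.2 defines both as gathered over the course of the study.

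**Missing entries.** Section 7 foresees them: "every effort will be made to contact participants who have failed to attend scheduled visits, submit requested information via the smart phone application". At least two telephone contacts are promised. Section 8.1 allows for 15% dropout and later mentions dropouts already observed. The one analysis rule for dropouts, in 8.2, counts them as failing the urate target or as non-compliant, so it covers only the binary outcomes.

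**Flare days.** Section 2.2.2 has the endpoint "Prospectively gathered number of days of self-reported gout flare over course of study". Section 8.2 does not list it among the measures to be analysed.

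**The concern.** A count gathered month by month depends on how many months were reported as well as on how often events occurred. A participant who reports for six months has, on average, half the total of one with the same event rate who reports for twelve. A t-test or Mann-Whitney on such counts cannot separate the two. If one arm leaves earlier or submits fewer entries, it appears to have fewer lost days and fewer appointments.

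There is reason to think reporting could differ. Controls have a limited version of the app (3.1). The intervention arm also gets urate-test reminders two weeks after each dose increase, and monthly requests once at target (6.1.2).

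Section 2.1.2 names hospital and GP visits and work absence as the data for cost-effectiveness. Section 8.1 says the study is to inform a larger cost-effectiveness study, and 13.2 promises a full cost analysis. A distorted count would carry into that work.

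**Working it through.** **The plan's own figure.** The documents give no power, event rate or reporting rate for these outcomes. The stated 82% power concerns the urate endpoint. It reproduces at 82.7% (Yates-corrected chi-square, 14 v 28, with 14/0.85 = 16.5 rounded up to 17 controls) and has no bearing here.

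**Inputs from the documents.** About 60 participants at 2:1, so 40 v 20; about 12 monthly entries in 52 weeks. **Assumed:** all reporting rates, event rates and between-patient spread.

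**1. Ratio of totals.** Expected total = rate × months reported. With equal rates, the ratio of totals equals the ratio of months:
- 11 v 9 months: 11/9 = 1.22, a spurious 22% excess in the arm that reports more.
- 11 v 6 months: 11/6 = 1.83, a spurious 83% excess.

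**2. Dropout alone.** Assume 10% v 25% dropout, spread evenly over the year, with no missed entries. Mean follow-up is 1 − 0.10/2 = 0.95 v 1 − 0.25/2 = 0.875 of a year. The ratio is 0.95/0.875 = 1.09, a 9% distortion.

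**3. False positives.** Simulation with no true effect: 40 v 20, each participant's rate drawn from a gamma distribution (mean 1 per month, shape 0.7), Poisson counts over the months reported, two-sided 5%. The ranges cover repeated independent runs.

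| Months reported | Mann-Whitney on totals | Mann-Whitney on totals ÷ months reported |
|---|---|---|
| equal | 4.5% to 5.5% | about 5% |
| 11 v 9 | 6.8% to 7.7% | about 5% |
| 11 v 6 | about 30% | 5% to 6% |

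The size depends on the spread. With a mean of 12 days a year and 90% v 75% of months reported, the false-positive rate on totals is 7.8% at shape 1 and 15% at shape 3. At 90% v 60% it is 22% and 54%. The t-test gives similar values.

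**4. Direction.** Suppose the intervention truly cuts the rate to 0.6 of control and reports more months. The ratio of totals is 0.6 × 11/9 = 0.73 at 11 v 9, and 0.6 × 11/6 = 1.10 at 11 v 6. The benefit shrinks in the first case and reverses in the second.

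**5. Limit of the remedy.** Dividing by months reported works if unreported months resemble reported ones. Suppose instead that only event-free months are skipped. Same settings, no true effect:
- 10.9 v 8.8 months: ratio of totals 1.00, false positives 4.7%; but the rate per reported month in the arm reporting less is 10.9/8.8 = 1.24 times that in the other.
- 10.9 v 6.2 months: ratio of totals 1.01, false positives 4.8%; but the rate ratio is 1.75, and Mann-Whitney on rates rejects in 46%.

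Totals are then right and rates are wrong, so neither analysis is safe alone.

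**The case against.** **Unequal reporting is not shown.** This stands. The dropout allowance is one overall figure and the documents give no split by arm. Both arms get the same request for these data: "All participants will be prompted once per month to enter information about their disease severity". The intervention arm's extra prompts ask for urate readings and, at target, stop after three consecutive target readings (6.1.2), so they need not span the year. With equal reporting there is no inflation. A reader might infer that the planned tests will create an apparent benefit of the intervention. The documents do not support that, and if controls report less, a benefit would be hidden.

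**Raw totals are not stated.** This stands in part. The plan never says how monthly entries are combined or whether partial reporters are included. Totals are the natural reading of a number gathered over the course of the study.

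**Flare days.** A reader might infer that they too are compared as raw totals. Section 8.2 does not say so. It names no analysis for them, and its wording may not be meant as a complete list. The gap is an unstated method.

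**Safeguards.** Telephone contacts (7), diary review at weeks 24 and 52 (6.1.3, 6.1.4) and the electronic patient record as a source (7.1) should reduce missing entries, and make a gap as wide as 11 v 6 less plausible. They do not say how to analyse what is still missing. The Bonferroni correction in 8.2 makes significance harder to reach but does not remove a bias in the estimate.

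**Conclusion.** The point holds in conditional form. For work days lost and appointments or admissions, 8.2 makes no allowance for dropout or missed months, and its only dropout rule does not extend to counts. If follow-up or reporting differs by arm, the arm with fewer reported months looks better. At an assumed 11 v 9 months the ratio is off by 22% with about 7% false positives; at 11 v 6 it is off by 83% with about 30%. These sizes rest on assumed reporting rates, on totals being what is compared, and on missed months resembling reported ones. Separately, flare days have an endpoint but no listed analysis.

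The change is worth making because these data feed the next study's cost work. It is not critical: the outcomes are exploratory, this is a feasibility study, and the primary endpoint is unaffected. Confidence is medium.

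**What to change.** In 8.2:
1. Add flare days to the listed outcomes. Analyse flare days, work days lost and appointments/admissions as rates, by negative binomial or quasi-Poisson regression with log(months reported) as offset. Give rate ratios with 95% confidence intervals.
2. Report months submitted and dropout by arm beside these results.
3. Add a sensitivity analysis that counts skipped months before withdrawal as event-free: the total count with log(months in follow-up) as offset. If the two analyses disagree, say that the result depends on what happened in the unreported months.

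The cost is a change of SAP wording and slightly more analysis; no new data are needed. The downside is a missingness assumption that cannot be tested. The two analyses cover skipped months that resemble reported ones and skipped months that are event-free. They do not cover months skipped because the participant was having a flare, and the report should say so.

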6 STUDY PROCEDURES AND ASSESSMENTS

6.1 STUDY PROCEDURES

6.1.1 Baseline visit

Written and informed consent will be obtained. A history will be taken, basic anthropometric measurements taken (blood pressure, weight, waist circumference) and physical examination be performed. Full medication history will be obtained from participants. Blood samples will be taken for measurement of urate, full blood count, renal and liver function and oxypurinol levels. A finger prick testing for urate levels will be carried out. Participants will be asked to collect urine over a period of 24hrs to hand into the lab as soon as feasible after the baseline visit. A blood sample for creatinine and urate will be taken at that point for paired analysis with urine. Eligible subjects will be randomised at a 1:2 ratio to usual care or supported self-management using a web-based randomisation tool.

For the purposes of the microbiome analysis, patients will provide a once off stool and urine sample at baseline in addition to filling an online food frequency questionnaire. For control subjects for the microbiome analysis, participants will attend on one occasion to provide written informed consent, medical history review, FFQ, blood samples for urate, renal and liver function and oxypurinol levels. In addition they will provide an early morning urine sample and a fresh faecal sample. They will also be asked to collect urine over the 24hour period and a paired serum renal function and urate blood sample will be taken when handing the collection in. No further follow-up visits are planned.

No payment shall be made for participation in the study but compensation for costs of travel to the Western General Hospital shall be offered to control participants up to a value of £30

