6.2 STUDY ASSESSMENTS

6.2.1 History and physical examination

A focussed history and physical examination will be carried out at the specified time points. This includes basic anthropometrics weight, height, waist circumference and blood pressure. We will be recording the presence of tophi and take measurements of the largest tophus. Details of the duration of disease, frequency and pattern of flares will be recorded.

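### Work days lost and gout-related health-care contacts are compared without adjusting for the flare frequency taken in the baseline history, which gives up some precision in two exploratory outcomes.

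*Combined protocol and SAP*

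**What the plan says.** Section 8.2 (Proposed analyses) lists the outcomes: "Further continuous outcomes include the number of days lost at work due to gout flare", followed in the same sentence by counts of medical appointments, both scheduled and unscheduled, and of hospital admissions. It then gives the tests. "Two-tailed independent student t-tests will be applied for between group comparisons of normally distributed data", and "A Mann Whitney U test (MWU) will be applied when the variables are not normally distributed". No covariate, stratified comparison or count model is planned for any outcome. Section 8.2 describes these measures as exploratory, sets a nominal 5% level, and adds that "given the number of secondary outcomes listed a Bonferroni correction will be applied and reported alongside each result".

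Two other sections make a relevant baseline predictor available. Section 6.2.1 (History and physical examination) says "Details of the duration of disease, frequency and pattern of flares will be recorded". Section 6.1.1 (Baseline visit) says "A history will be taken, basic anthropometric measurements taken (blood pressure, weight, waist circumference) and physical examination be performed". Read together, they put flare frequency in the baseline record, although no look-back period is given for it.

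On allocation, section 6.1.1 says "Eligible subjects will be randomised at a 1:2 ratio to usual care or supported self-management using a web-based randomisation tool". No stratification factor is named there or elsewhere.

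**The concern.** Both outcomes are defined by gout: working days lost because of flares, and health-care contacts because of gout. A person who flared often before randomisation can be expected to flare more often afterwards, so prior flare frequency is a natural predictor of both. No baseline measure of work loss or contacts is planned, which leaves flare frequency as the obvious covariate already being collected.

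An unadjusted comparison has two costs. It keeps between-person variation that the covariate could explain. It also leaves in the estimate any difference in prior flare burden that arises by chance, and with 17 controls such differences are not rare.

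The outcomes have a use beyond description. Section 2.1.2 makes cost-effectiveness, informed by health-care visits and work absence, a secondary objective. Section 8.1 says the study is to inform a larger cost-effectiveness study, and section 13.2 promises a full cost analysis.

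**Working it through.** **The plan's own figure.** The plan states no power for work days or contacts. Its 82% (section 8.1) is for the primary endpoint, 25% v 75%, with 34 + 17 randomised and 15% drop-out. The continuity-corrected two-proportion formula needs 28 + 14 completers. Dividing by 0.85 gives 33 + 17, against 34 + 17 stated. Power at 28 + 14 is 82.1%, so the figure reproduces. It is not affected by this point.

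**Inputs.** From the documents: 34 intervention and 17 control, no stratification named. Assumed: *r*, the correlation between baseline flare frequency and the outcome, taken as 0.3 to 0.6.

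**Step 1: chance imbalance.** For a standardised covariate, SD of the difference between arms = sqrt(1/34 + 1/17) = 0.297.
- P(imbalance above 0.25 SD) = 2 × [1 − Φ(0.25/0.297)] = 40%.
- P(imbalance above 0.5 SD) = 2 × [1 − Φ(0.5/0.297)] = 9% (13% with 28 + 14 completers).

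**Step 2: precision.** Adjustment multiplies the variance by 1 − r², so it is worth 51/(1 − r²) unadjusted participants. The detectable difference is for 80% power, two-sided 5%, noncentral t; unadjusted it is 0.85 SD.

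| r (assumed) | Variance removed | SE reduced by | Equivalent N (actual 51) | Detectable difference, adjusted |
|---|---|---|---|---|
| 0.3 | 9% | 4.6% | 56 | 0.81 SD |
| 0.5 | 25% | 13.4% | 68 | 0.74 SD |
| 0.6 | 36% | 20.0% | 80 | 0.68 SD |

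**Step 3: effect of an imbalance of exactly 0.5 SD.** With no treatment effect, the unadjusted difference is shifted by 0.5r and has conditional SD s = 0.297 × sqrt(1 − r²). The conditional error is 1 − Φ[(1.96 × 0.297 − 0.5r)/s] + Φ[(−1.96 × 0.297 − 0.5r)/s].
- r = 0.3: shift 0.15 SD, error 6.8%.
- r = 0.5: shift 0.25 SD, error 9.9%.
- r = 0.6: shift 0.30 SD, error 11.8%.

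**Step 4: error over all randomisations.** In simulated overdispersed counts at 34:17 (4,000 trials per setting, gamma-distributed flare rates, no treatment effect), Mann-Whitney rejected in 4.5% to 4.8% and rank ANCOVA in 4.8% to 5.0%. Both tests hold their level.

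**Step 5: power for counts.** In the same simulation with an assumed rate ratio of 0.4, power was 36% for Mann-Whitney v 45% for rank ANCOVA at a rank correlation near 0.5, 18% v 20% near 0.33, and 21% v 22% near 0.22.

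**Step 6: work days when some participants do not work.** Someone not in work loses no days however often they flare, which weakens the correlation. Assumptions: 34:17, 60% employed, means of 4 baseline and 3 follow-up flares, flare rate halved, 3,000 trials.

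| Setting | Mann-Whitney | Rank ANCOVA | Gain |
|---|---|---|---|
| One day lost per flare, gamma shape 1 | 15.0% | 17.6% | 2.6 points |
| Variable days per flare, shape 1 | 14.6% | 16.0% | 1.4 points |
| Variable days per flare, shape 2 | 17.1% | 17.7% | 0.6 points |

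The Monte Carlo SE of each power is about 0.7 points, for example sqrt(0.15 × 0.85/3000) = 0.0065. With no effect and an imbalance above 0.5 SD, Mann-Whitney rejected in about 6% to 9%.

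**The case against.** The strongest reply is that nothing here is wrong. Both planned tests are valid, the outcomes are labelled exploratory, a Bonferroni correction is reported beside each result, and the trial is a feasibility study that makes no power claim for work loss or contacts. Planning a larger study mainly needs arm-level means and SDs, which adjustment does not change. All of this stands. Bonferroni, however, deals with multiplicity; it does not restore precision or remove an imbalance.

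The reply also holds that the predictor may be weak. Section 4.2 does not require employment. Section 8.2 counts scheduled as well as unscheduled appointments, and scheduled ones need not follow flares. Flare frequency is recalled, with no stated look-back, so a standardised covariate does not yet exist. This stands too, and it is why the gain for work days may be only a few points.

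A reader might infer something stronger: that the unadjusted comparison is biased, or that its false-positive rate is well above 5%. The documents do not support that. Randomisation protects the comparison, and overall error is about 5%. Simulating flare counts themselves, with no effect and an imbalance above 0.5 SD, gives conditional error as high as 22% and, for a halved flare rate, power gains of about 6 to 22 points depending on the assumed flare means and dispersion. But flare counts are neither of these two outcomes, and an imbalance that large arises in only about 9% of trials.

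**Conclusion.** The point holds as a modest loss of precision. A plausible predictor is collected at baseline and left out of the comparison of two outcomes that section 8.2 tests formally. If r lies between 0.3 and 0.6, adjustment is worth roughly 5 to 29 extra participants on 51 (56 − 51 and 80 − 51). If many participants are not in work, the gain for work days falls to about 1 to 3 power points.

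The size rests wholly on r, the employment rate and the dispersion of flares, none of which the documents give. The raised error in step 3 applies only to trials in which such an imbalance occurs; it is not systematic bias. The primary endpoint and its 82% power are untouched. This is a minor improvement.

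**What to change.** In section 8.2, prespecify baseline flare frequency as a covariate for days lost at work and for appointments/admissions, and name one method:
- rank ANCOVA (Quade's test) in place of the plain Mann-Whitney test; or
- a negative binomial model with log(baseline flares + 1) as covariate and an offset for months observed, since section 6.2.3 collects these data monthly and section 8.1 expects drop-out.

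State one look-back period for the flare item in section 6.2.1. If enrolment is complete, use the item as recorded. Analyse work days among participants in work where employment status is known; the documents do not list it as a collected item. Keep the unadjusted test as a secondary display.

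The cost is one more prespecified model, a few sentences of text, and some recall noise in the covariate. No extra visits or participants are needed. Fixing the covariate before the data are seen also prevents a later decision to adjust only because an imbalance has appeared.

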3.2 Extension phase

Urate-lowering therapy requires a long term commitment from the patient and health care provider. We know that levels of medication adherence in gout are unusually low (Dehlin M, 2017 and Briesacher BA, 2008). A recent randomised controlled trial comparing specially trained nurses leading care versus usual care in the UK, showed that with dedicated surveillance and monitoring, the use of urate lowering therapy is significantly higher at 1 and 2 years in the nurse-led compared to the usual care group (Doherty M, 2018). The GoutSMART approach may provide an alternative means for patients to monitor their disease and increase awareness of the role and importance of long-term urate lowering therapy for disease control thereby increasing adherence. At the 12 month study visit all participants will be invited to participate in a 2 year extension to the study which will evaluate long term compliance with medication along with clinical outcomes. Additional participants will be invited to take part in

this long term monitoring arm of the study and will be randomised 1:1 to active monitoring or routine care. All participants taking part in this extension study will have their medication optimised using the GoutSMART approach to ensure that their urate level is at target of 0.3mmol/l or less.

For participants in the active care arm of the study ongoing monitoring of self-reported urate will be performed until participants meet criteria for disease remission. For the purposes of this study we will define disease remission to have been achieved if all three of the following outcomes have been achieved:

[figure not shown]
- 1) Resolution of clinically evident tophi
- 2) Urate levels at or below 0.3mmol/l over preceding 12 months (with minimum of 3 separate readings obtained in different months).
- 3) Resolution of gout flares (self-reported) for 12 months

When remission has been achieved by these criteria then participants will be given the option to reduce their dose of allopurinol in line with current best practise guidelines which suggest that maintaining urate below 0.36 mmol/l is sufficient to maintain remission, and that long term urate levels should not be held below 0.18mmol/l.

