8 STATISTICS AND DATA ANALYSIS

8.1 SAMPLE SIZE CALCULATION

This is a feasibility study which is intended to establish whether the proposed self-management approach can be realised in practice, and if so to inform the design of a larger study that would look to establish the cost-effectiveness of this approach.

The numbers chosen are based on previous audits in primary care performed which revealed that only 24% of gout patients reached a target of 0.30mmol/l of serum urate when receiving standard care by GPs who were given an algorithm for management of gout beforehand. We have assumed that about 25% of patients assigned to routine care will achieve the target of 0.3mmol/l in the control group. We are anticipating that we will achieve target levels of urate in 75% of patients in the intervention group which though ambitious is still well below the 92% achieved in a recent UK study (Rees, F. 2013). Based on these estimates a sample size of n=34 in the intervention group and n=17 in the control group (2:1 randomisation) provides 82% power to detect an effect of 25% in the control group and 75% in the intervention group (assuming a two-sided 5% significance level), after taking into account a 15% drop-out rate.

For the extension study we have assumed that 90% of participants in the Smart care arm of the study remain adherent to therapy, compared with only 50% in the usual care arm. These figures are conservative compared to 95% compliance reported in Doherty et al (2018) and 36.8% medicine possession ratio reported in Briesacher et al (2008). A sample size of 20 in each allocation yields 81% power, and 30 in each treatment allocation 94% power to detect such a difference. Due to observed drop outs from the feasibility study and restrictions in recruiting participants during the COVID pandemic we will recruit additional participants into the extension phase of the study to ensure sufficient power is achieved.

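### Section 8.2 should name the Welch form of the t-test: under 2:1 allocation the pooled form gives a wrong standard error if the arms differ in spread (minor)

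*Combined protocol and SAP*

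**What the plan says.** Section 8.2 names five continuous outcomes: index tophus size, number of tophi, work days lost, medical appointments or admissions, and medication doses missed in the two weeks before a visit. For these, "Two-tailed independent student t-tests will be applied for between group comparisons of normally distributed data". The alternative is set by distribution: "A Mann Whitney U test (MWU) will be applied when the variables are not normally distributed". Nothing is said about unequal variances, and results are to be shown as mean and SD by arm.

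The outcomes are exploratory: a "nominal value of significance of $p<0.05$ for these exploratory measures will be adopted", and "given the number of secondary outcomes listed a Bonferroni correction will be applied and reported alongside each result". The number of tests in that correction is not given.

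Allocation in the original study is unequal. Section 6.1.1: "Eligible subjects will be randomised at a 1:2 ratio to usual care or supported self-management using a web-based randomisation tool". Section 8.1 plans "n=34 in the intervention group and n=17 in the control group (2:1 randomisation)". Participants added for the extension are handled differently. Under section 3.2 they "will be randomised 1:1 to active monitoring or routine care".

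Binary outcomes (urate target, undetectable oxypurinol) use chi-square or Fisher's exact test.

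**The concern.** Student's independent t-test, as the name is ordinarily used, estimates one common variance from both arms. With equal arms this does little harm when the variances differ. With a 2:1 split the larger arm dominates the pooled variance. If the smaller usual-care arm is the more variable, the standard error is too small and the test rejects too often. If it is the less variable, the standard error is too large and power is lost.

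Unequal spread is plausible here. Section 8.1 expects 75% v 25% at urate target, and only the intervention arm receives self-testing and titration prompts. Outcomes bounded at zero often become less spread out as they move towards zero. That is inference, because no SD is given for any outcome in either arm.

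At stake are the p-values, raw and Bonferroni-adjusted, for outcomes analysed by t-test in a study meant to inform a larger trial. If the word Student is instead read as leaving the variance form open, a choice that changes p-values has not been fixed in advance.

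**Working it through.** **Arm sizes and the plan's own figure.** Section 8.1 gives 34 and 17, 25% v 75%, two-sided 5%, 15% drop-out and 82% power. After drop-out: 34 × 0.85 = 28.9 and 17 × 0.85 = 14.45. The continuity-corrected normal approximation at 28 v 14 is

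z = [0.50 − ½(1/28 + 1/14) − 1.96 √(p̄(1 − p̄)(1/28 + 1/14))] / √(0.1875 (1/28 + 1/14)), with p̄ = (28 × 0.75 + 14 × 0.25)/42 = 0.583.

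This is (0.500 − 0.054 − 0.316)/0.142 = 0.918, so power is 82.1%. At 29 v 14 it is 82.7%. The stated 82% reproduces. It concerns the primary endpoint and is not affected by this point. The t-test was checked at 34 v 17, at 29 v 14 (after drop-out), and at 40 v 20 (the target of about 60 in section 4.1, split 2:1).

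**Formula.** Let the intervention SD be 1 and the usual-care SD be r.

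- True variance of the mean difference: 1/34 + r²/17.
- What the pooled form estimates in large samples: 1/17 + r²/34. The two sample sizes change places.
- Ratio: k = (2 + r²)/(1 + 2r²).
- Actual two-sided error at nominal 5%: 2[1 − Φ(1.96 √k)].

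Example, r = 2: k = 6/9 = 0.667 and √k = 0.816, so the standard error is about 18% too small. 1.96 × 0.816 = 1.600, and the error is 10.95%. With equal arms k = (1 + r²)/(1 + r²) = 1 for every r, so the fault comes from combining unequal allocation with unequal spread.

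**Simulation.** Normal data, equal means, 34 v 17, 200,000 runs per setting. The SD ratios are assumptions.

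| SD ratio, usual care / intervention | k | Formula, pooled | Simulated, pooled | Simulated, Welch |
|---|---|---|---|---|
| 0.5 | 1.500 | 1.64% | 1.75% | 4.95% |
| 1 | 1.000 | 5.00% | 4.95% | 4.96% |
| 1.25 | 0.864 | 6.85% | 6.80% | 4.96% |
| 1.5 | 0.773 | 8.49% | 8.47% | 4.99% |
| 1.75 | 0.711 | 9.85% | 10.13% | 5.05% |
| 2 | 0.667 | 10.95% | 11.17% | 4.97% |
| 3 | 0.579 | 13.59% | 14.26% | 5.04% |

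At ratios 1.5 and 2 the pooled form gives 8.8% and 11.6% at 29 v 14, and 8.4% and 11.1% at 40 v 20. Recruiting more at 2:1 does not cure it.

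**Bonferroni.** The number of tests is assumed. At ratio 2 with five tests the pooled form rejects 3.6% of the time against 1.0% intended. With ten tests it is 2.2% against 0.5%. The correction does not repair the fault.

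**Cost of Welch.** With equal variances at 34 v 17 and a true difference of 0.8 SD, power is 75.2% (pooled) and 74.4% (Welch), a loss of 0.8 points.

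**The case against.** Four arguments count against making much of this.

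**The null and the variance gap come from different scenarios.** If the intervention does nothing to an outcome, randomisation gives both arms the same distribution and there is no gap. If it lowers and narrows the outcome, the means differ and a rejection is not a false positive. This limits the type I framing, but it does not remove the fault, because the pooled standard error is wrong whether or not the means differ. With normal data, a pooled 95% interval at ratio 2 covers about 100 − 11 = 89%, and at ratio 0.5 about 100 − 2 = 98%, whatever the true difference.

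**Most of the named outcomes will probably not reach the t-test.** Four of the five are counts, likely to be skewed with many zeros, and section 8.2 sends non-normal data to Mann-Whitney. This stands. Index tophus size is the main candidate, and section 6.1.2 records tophi only where present, so its sample is smaller than 34 v 17. The Welch wording also does nothing for the Mann-Whitney branch, which itself gives 6.8% and 8.5% at ratios 1.5 and 2 with normal data.

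**Welch is not exact everywhere.** With assumed negative binomial counts (mean 1 to 2, dispersion 0.3 to 1) and no treatment effect, the pooled test gives 4.0–4.7% and Welch 5.3–5.6%. In an assumed 10 v 5 subset with tophi, Welch gives 5.4–5.6% at ratios 1.5 to 3, against 8.6–15.7% for the pooled form. This stands as a small qualification.

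**The consequences are limited.** The outcomes are exploratory in a feasibility study, and the additional extension participants are randomised 1:1. This stands and sets the priority.

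**Conclusion.** The point holds as a minor clarification. Section 8.2 names Student's t-test subject only to normality, in a study randomised 2:1. If the arms differ in spread, the pooled form is miscalibrated in either direction: about 7%, 8.5% and 11% at assumed SD ratios of 1.25, 1.5 and 2, and about 2% at 0.5, where Welch holds about 5%. These figures rest on normal data, 34 v 17 and assumed ratios.

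A reader might infer three stronger things that the documents do not support:

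- **That the error rate doubles.** This needs a usual-care SD about 1.75 to 2 times the intervention SD, and the documents give no SD.
- **That the secondary outcomes as a whole are affected.** The binary ones use chi-square or Fisher, and most of the continuous ones probably go to Mann-Whitney.
- **That the plan has committed to equal variances.** Pooling is the ordinary meaning of the test's name, but section 8.2 does not state the variance form.

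The primary endpoint and its power calculation are untouched.

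**What to change.** In section 8.2, state that wherever a t-test is used for a between-arm comparison it is the Welch (unequal-variance) form, and that the mean difference is reported with its Welch 95% confidence interval alongside the planned mean and SD. Leave the Mann-Whitney branch as it is.

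This is one phrase and one added reporting item, with no change to design, sample size or data collection. The price is about one percentage point of power if the variances are equal, and an error slightly above 5% (about 5.3–5.6%) in very small subsets or skewed counts.
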